STARCHy staples: a randomised controlled trial on Cardiometabolic Health.

Clinical Trials ref: NCT05994313

REC: HR/DP-22/23-35587

Version number: 5.1

31 August 2025

Short title/ Acronym: The STARCHy study.

Abbreviations

CGM - Continuous Glucose Monitor
ECG – Electrocardiogram
HRV – Heart Rate Variability
BP- Blood pressure
FMD – Flow mediated dilation
VAS – Visual analogue scale

1. Trial summary

Responsible Individuals

Principal Investigators

[name]
Reader in Nutritional Sciences
Franklin Wilkins Building
Faculty of Life Sciences and Medicine
Department of Nutritional Sciences
[name]
Email: [name]

[name]
Reader in Nutritional Sciences
Franklin Wilkins Building
Faculty of Life Sciences and Medicine
Department of Nutritional Sciences
[name]
Email: [contact]

PhD researcher and trial coordinator

[name]
[name]
Faculty of Life Sciences and Medicine
Department of Nutritional Sciences
[name]
Email: [contact]

Collaborators

[name]
[name]
[name]
[contact]
E-mail: [contact]

[name]
Chemical and Biological Engineering
Rensselaer Polytechnic Institute, [name]
E-mail: [contact]

Study Synopsis

Title	STARCHy staples: a randomised controlled trial on Cardiometabolic Health
Protocol Short Title/Acronym	The STARCHy study
Protocol Version number and Date	Version 5: 20/08/2025
Study Phase if not mentioned in title	n/a
Is the study a Pilot?	No
Study Site	In-person visits: Metabolic Research Unit, [name] Remote video calls via Teams
Study Duration	24-months
Official study start date	09/09/2023
Estimated Primary Completion	01/05/2025
Methodology	A randomised, two-parallel arm, in clinic and remote, 12-week dietary intervention, with a 2-week run in period. Participants will either receive 230g of potatoes in their evening meal (intervention) or isocaloric amounts of other refined starchy staples, such as rice, pasta, or couscous (control). Participants will make their own meals based on dietary guidance and resources (meal plans), given from a registered nutritionist, to match UK recommendations.
Sponsor name	King's College London

Chief Investigator	[name] and [name]
REC number	22/23-35587
Medical condition or disease under investigation	Cardio-metabolic health
Purpose of clinical trial	To investigate the cardio-metabolic health effects of consuming potatoes in place of other refined carbohydrate (pasta and rice), in healthy adults.
Primary objective	The primary objective of this proposal is to investigate whether consuming a portion of potatoes in the evening meal, in place of other refined carbohydrates, can improve sleep quality (measurable as the ratio of total sleep time in bed: "sleep efficiency"), and improve mean nocturnal glucose, both risk factors for cardiometabolic diseases.
Secondary objective (s)	To investigate the effects of regular white potato consumption on endothelium-dependent vasodilation (measured by flow-mediated dilatation) and other related biomarkers of cardio-metabolic disease risk, when compared to regular refined carbohydrate consumption.
Number of Participants	The study aims to recruit a total of 80 participants (allowing ~15% drop out rate), for an allocation of 1:1 intervention to control, to reach 80% power at a significance level of 0.025 (based on two outcomes).
Trial Design	A randomised, two-parallel arm, in clinic and remote, 12-week dietary intervention study.
Study arms	
1. Experimental: Habitual potato consumption.
 
At minimum of 230g white potatoes, including fresh and frozen, baked, boiled and mashed potatoes, will be consumed in the evening meal, in replacement of other starches.
 
2. Active Comparator: Habitual non-nutrient dense starch consumption.

	Isocaloric amount of non-nutrient dense starchy staples, such as white rice, white pasta, and white couscous, will be consumed during the evening meal.
Endpoints	
Primary
 
 • 7-day Sleep efficiency, at baseline and endline • 12-day nocturnal mean glucose (using Continuous Glucose Monitors (CGM) during sleep), at baseline (0 weeks) and endline (12 weeks) 
Secondary
 
 • Endothelium-dependent vasodilation (measured by ultrasound image analysis as Flow-Mediated Dilation (FMD)), at baseline and endline. • 12-day daytime and 24-hour glucose metabolism (CGM outcomes, glycaemic variability, time in range). • 48hrs nocturnal, daytime and stress-related heart rate variability (measure of autonomic function; higher range the more autonomic function) • 12-week daytime and night-time continuous blood pressure (Aktiia blood pressure bracelet) • Blood parameters 
 ◦ Glucose control (fasting HbA1C, fasting glucose and insulin) ◦ Lipids • Body composition 
 ◦ weight and waist circumference ◦ % body fat and lean body mass (Tanita scales) • Visual Analogue Scale (VAS) assessments of satiety, included in 4-day diet diaries. • Urinary potassium and sodium • Urinary alkaloids (calystegines) 
Compliance
 
 • Urinary potassium and sodium • Dietary assessments 
 ◦ 24-hour recall (Wk 2, 4, 8) ◦ 4-day food diary (Wk 0, 6, 12) ◦ Self-reported adherence: checklist of evening meal
Main Inclusion Criteria	Participants will be healthy male or females, aged between 40-80 years who consume ≤4 fruits and vegetables a day (excluding potatoes), with a less favourable sleep efficiency score of <85%

Statistical Methodology and Analysis	
Differences between groups (minimized for age, gender, BMI) will be analysed using Linear mixed models for outcomes with 3 timepoints (urinary outcomes, dietary intake data), with change being the dependent factor, participant ID as random effect, treatment and season as fixed effects, and baseline outcome and BMI as covariates. Variables with 2 timepoints will be assessed with an ANCOVA regression model.
 
A 2 -sided P value <0.05 will be considered as showing statistical significance.
 
For more details of statistical analysis plan, see section 4.2.

Data monitoring and sharing	
No formal data monitoring committee. Oversight by PI and sponsor.
 
De-identified data will be shared upon reasonable request and in collaboration with the study investigators, beginning 12 months after publication of the main trial results.

2. Introduction

2.1 Background

There are several studies currently underway to explore the CM health effects of diets rich in potatoes on glucose metabolism, lipids, inflammation, and blood pressure/vascular function. However, to our knowledge, none investigate the potentially favourable impact of potatoes on the harmful triad of **poor sleep - adverse glycaemic control - vascular dysfunction**.

Poor sleep quality is related to adverse glycaemic control: can increasing potassium intake help?

The deleterious impact of poor sleep on diet, obesity and CM health (1) has been consistently reported in observational and interventional studies (2). Potential mediating mechanisms include; impaired endothelial function (3), perturbed postprandial (4) and nocturnal glycaemic responses (5), raised blood pressure, and bi-directional associations between diet and poor sleep quality (6). Results from the PREDICT 1 cohort (n=1102) showed that participants with higher sleep efficiency (i.e. better sleep quality), measured objectively using wrist actigraphy, had lower postprandial blood glucose the next day following a standardised test meal than those with low sleep efficiency, and this relationship was replicated upon within-participant analysis, suggesting that better sleep quality could lead to improved glycaemic control in healthy individuals (4). This potential causal link between poor sleep quality and adverse glycaemic control may be mediated via poor diet quality in free-living conditions, as inadequate sleep increases cravings for less healthy foods (7) (and vice versa, poor dietary choices may impact on sleep quality (6)). However, there may also be a direct effect by increasing sympathetic outflow thereby suppressing insulin secretory responses to fluctuations in glucose (8).

High dietary glycaemic index (GI) is associated with greater subsequent risk of insomnia (9) whereas higher intakes of fruit, fibre and vegetables (9, 10, 11) are associated with better sleep quality. The effects of fruits and vegetables on sleep quality have been suggested to be related to their polyphenol, melatonin, and serotonin contents (6), but little attention has been paid to their potassium content as a putative sleep quality promoter. Preliminary data analysis using our PREDICT cohort show that there is a positive association between potassium intakes and sleep duration ($P=0.02$) and an inverse

association between fasting glucose and glycaemic variability with potassium intakes ($P=0.03$, $P=0.04$) respectively, adjusted for age, sex, BMI and energy intake. This requires further investigation as regards to the source of potassium and adjusting for background diet, as proposed in this application. Potassium may plausibly modify sleep quality (12), glycaemic control (via insulin secretion (13)) and cardiovascular function (14) by modifying autonomic function. For example, potassium supplementation in rats with chronic heart failure reduces sympathetic overactivity and restored baroreflex function (15) and reduces risk of CVD mortality (16) and reduces blood pressure in human studies (17, 18), the latter mediated in part by preservation of autonomic function (19), as well as reduction in renal sodium reabsorption and stimulation of endothelium-dependent vasodilation.

Endothelial function: can increasing potassium help?

Sufficient dietary potassium may improve sleep quality and glycaemic control, and consequently this may support better endothelial function. Poor sleep quality has been reported to be associated with lower FMD in a cohort of healthy adults (20) and restricting sleep by one-third causes endothelial dysfunction in healthy individuals (21). Likewise, oscillating blood glucose concentrations in healthy volunteers led to impaired endothelial function, likely to be mediated via vascular inflammation and oxidative stress (22). However, there is also evidence that potassium could directly act on the endothelium to increase nitric oxide production (and thus endothelial function) (14, 23), which could also potentially benefit autonomic function by enabling greater nitric oxide bioavailability in the brain as well as the blood vessels (24).

Potassium intakes and potato consumption in the UK and US

Low population dietary intake of potassium is a point of concern in both the UK (median intake 79% of the reference nutrient intake) and US. However, potatoes are the greatest contributors of dietary potassium for a single food (UK and US), contributing 14% of intakes in UK 19-64 y olds (consumers and non-consumers) (25) and 20% of intakes in US (for consumers) (26). Although regarded as a high glycaemic index food, potatoes that were boiled, roasted, or boiled then cooled, resulted in markedly lower nocturnal interstitial glucose concentrations compared to rice in individuals with type 2 diabetes despite there being no glycaemic differences in the acute postprandial period (27). Potatoes are rich in micronutrients, unlike commonly consumed starchy staples such as white rice and pasta. In addition to potassium, potatoes contribute 15% of vitamin B6 intake, 14% of vitamin C and 10% of folate in the UK (28), and therefore contain a range of components that may additively improve glucose metabolism, endothelial function and sleep quality beyond the immediate postprandial period.

2.2 Hypothesis and rationale

In the long term, a potato-rich diet could be an important strategy for reducing risk of CM diseases. This proposal aims to unravel an array of understudied CM health variables that may be beneficially affected by habitual consumption of nutrient-dense white potatoes.

We hypothesise that regular consumption of potatoes in place of other less nutrient-dense starchy foods increases sleep efficiency, reduces nocturnal glycaemic variability, and improves endothelial function in middle-aged to older adults.

To establish causality between potato consumption and these outcome measures, including mediating mechanisms, we plan to conduct a randomised, two-parallel arm-controlled trial in healthy adults between the ages of 40-80 years.

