3.3 Outcome variables

Primary Outcomes

Sleep efficiency: As aforementioned, increased dietary potassium may plausibly modify sleep quality, as previously seen in an interventional study by Drennan et al (46), through mediation of improvements to autonomic function (19) and improved vascular function by restoring baroreflex function (15) and improving endothelium-dependent vasodilation (47).

This is measured by using 7-d wrist actigraphy (MotionWatch8, CamNTech Ltd, Cambridge, UK) according to previously published procedures (7). Sleep quality (%) is measured as the amount of time spent asleep/ total amount of time spent in bed.

12-day mean nocturnal glucose: Potatoes may improve nocturnal glucose through several pathways, involving increased dietary quality (48), such as increased vitamin C (49), increased dietary potassium (50) and increased satiety, when compared to alternative starches (51).

Nocturnal measures were chosen to assess glycaemic regulation without the confounding influence of food intake. Whole sleep-time glycaemia parameters will be analysed is, and further sub analysis will

be done pre- and post-sleep, and mid-point to investigate potential differences according to sleep stages.

CGM (Abbott Freestyle Libre 3) will be used to measure glycaemic control for 12 consecutive days. The principal investigators have recently reported on the high precision of the Abbott CGM (52). Twelve days has been selected as the 1st and last day of the CGM period may give unreliable results, therefore day 1 and 14 will be excluded from the analysis.

Secondary outcomes

Other nocturnal glucose markers: We will further analyse 12-day nocturnal area under the curve, glycaemic variability (GV), time in range non-diabetic population (TIR_{ND}). GV reflecting glucose fluctuations, are more strongly associated with oxidative stress than prolonged elevated glucose and glucose nadir and peaks, including the number and size (% change from pre-meal baseline) due to the association of glucose nadirs with hunger, satiety, alertness and energy intake (at subsequent meals and over 24 h period) (53) and peaks with oxidative stress and impairment in glycaemic control. Increased TIR_{ND} is associated with improved cardiometabolic markers (lower HbA1c, HOMA-IR, and 10-y ASCVD risk) and with poorer glucose tolerance when TIR is low (higher 1- and 2-h OGTT glucose) (54).

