Daytime glycaemic control: Additionally, we plan to look at the same markers across 12-day daytime and 24-hour period.

Endothelial function: Impaired nitric oxide (NO) production causes endothelial dysfunction and increases risk of CVD (55). Capacity to synthesize NO can be assessed by ultrasound imaging of brachial arterial diameter before and after hyperaemia to determine FMD, regarded as the most reliable *in vivo* index (56). Measurements (and blood samples) will be taken at the same approximate time of day to account for circadian fluctuations, and by the same operator to reduce measurement error. All videos will be analysed using a custom MATLAB program (VidArt V13.5, [name], Department of Biomedical Engineering, Maastricht University Medical Center (MUMC)+, Maastricht, The Netherlands)

Heart rate variability (HRV) and blood pressure (BP): Improved HRV, a parameter of cardiac autonomic function, and BP are plausible health benefits of white potato consumption due to increased potassium intakes. Previous intervention studies have reported an improvement in clinic BP following potato consumption (18); however, the effects of potato intake on HRV have not been investigated to our knowledge. HRV is an indirect measure of autonomic nervous system function and predictive of risk of sudden cardiac death (57).

HRV will be measured using a small wireless heart rate/ECG monitor that continuously records interbeat intervals (eMotion Faros 180, Mega Electronics Ltd) to calculate 48-h, daytime and night-time parameters using Cardiscope Analytics software (HASIBA Medical GmbH) (58) Building on prior HRV analysis expertise (58, 59, 60), this will provide novel data on a hitherto unexplored risk factor for hypertension, T2D, chronic kidney disease and CVD events in relation to potato consumption, and will provide important mechanistic information underpinning the 3 primary outcomes. BP will be measured at home using optical blood pressure monitoring via a bracelet. 2-hour averages will be obtained continuously for 12-weeks.

Diet quality will be measured using dietary indices associated with health including PDI (61) (uPDI, hPDI), aMED (62), aHEI (62) and HFD (63, 64) to demonstrate the impact of potatoes on overall diet quality and for inclusion as a covariate in analysis.

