4.0 Sample Size, Statistics, Selection and Withdrawal of Participants

4.1 Sample size

This study aims to recruit a total of 80 men and women, 1:1 intervention to control, to have 68 people (~15% dropout) complete the study. 34 people in each arm will provide 80% power to detect a difference of 0.468 mmol/L nocturnal glucose concentrations (SD 0.61), based on our CGM data from PREDICT 1 (unpublished data). Additionally, only 24 people are needed to provide 80% power to detect a difference of 4.2% sleep efficiency units, with SDs based on our previous sleep extension intervention (SLuMBER study) (7). These parameters are based on a significance level of 0.025, for two outcomes (calculated with *G*Power* software)

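### The hypothesis in Section 2.2 and the designated primary endpoints share only sleep efficiency, and Section 3.3 counts three primary outcomes where two are listed

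*Combined protocol and SAP*

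**What the plan says.** Section 2.2 gives the trial's general hypothesis: potatoes in place of less nutrient-dense starches "increases sleep efficiency, reduces nocturnal glycaemic variability, and improves endothelial function in middle-aged to older adults". The next sentence sets out the reason for the trial: "To establish causality between potato consumption and these outcome measures, including mediating mechanisms". Mean nocturnal glucose is not mentioned there.

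The formal lists differ from this:

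- The Study Synopsis (Endpoints) names two primaries: "7-day Sleep efficiency, at baseline and endline" and "12-day nocturnal mean glucose (using Continuous Glucose Monitors (CGM) during sleep"). The synopsis primary objective names the same two.
- Section 3.1 poses two primary questions. The first is about sleep efficiency. The second is about glycaemic control at night and names no metric. Endothelial function is the first secondary question.
- Section 3.3 puts sleep efficiency and 12-day mean nocturnal glucose under its primary heading. Variability comes under the secondary heading: "We will further analyse 12-day nocturnal area under the curve, glycaemic variability (GV").
- Section 3.3, in the paragraph on heart rate variability and blood pressure, describes mechanistic information "underpinning the 3 primary outcomes". It does not name the three.
- Section 4.1 sizes the trial on mean glucose: "34 people in each arm will provide 80% power to detect a difference of 0.468 mmol/L nocturnal glucose concentrations", at 0.025 for two outcomes.
- Section 4.2 and the synopsis set one significance threshold, two-sided P<0.05, with no split between primary and secondary outcomes.

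Section 5.91 separately predicts a higher FMD in the potato arm, without saying what status that prediction has.

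**The concern.** A confirmatory trial should have one hypothesis that its primary endpoints test. Here two of the three hypothesised effects are secondary outcomes, and one of the two primaries is missing from the hypothesis. Mean and variability are different quantities: a result on the mean neither confirms nor refutes a claim about variability.

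What is at stake is the claim made at the end. Suppose mean nocturnal glucose shows no difference but variability or FMD reaches P<0.05. A report could then say, accurately by the wording of Section 2.2, that part of the trial's hypothesis was supported. That support would rest on an outcome with no share of alpha and no power calculation. Section 4.2 contains no rule confining confirmatory claims to the primaries. The unspecific second question in Section 3.1 leaves the same opening, because a variability result could be offered as its answer. The count of three in Section 3.3 makes it harder for a reader to see which set governs.

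**Working it through.** **1. Does the stated sample size belong to the two-primary set?** Inputs from Section 4.1: difference 0.468 mmol/L, SD 0.61, power 80%, alpha 0.025 for two outcomes, 68 completers, about 15% dropout.

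- Standardised difference: d = 0.468/0.61 = 0.767.
- Normal approximation, two-sided 0.025: n = 2(2.241 + 0.842)²/0.767² = 19.01/0.5886 = 32.3, so 33 per arm.
- Exact noncentral t, the usual calculation in the software the protocol names: 34 per arm, with power 80.5%.
- Dropout: 68/(1 − 0.15) = 80.
- At two-sided 0.05 the t calculation gives 28 per arm, so the plan's 34 comes from 0.025.

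The plan's 34, 68 and 80 are reproduced. They belong to mean nocturnal glucose as one of two primaries.

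**2. Status of each outcome.**

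| Outcome | In Section 2.2 hypothesis | Listed status | Sized in Section 4.1 |
|---|---|---|---|
| Sleep efficiency | Yes | Primary | Yes |
| 12-day mean nocturnal glucose | No | Primary | Yes |
| Nocturnal glycaemic variability | Yes | Secondary | No |
| Endothelial function (FMD) | Yes | Secondary | No |

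Only the first row is both hypothesised and primary. Variability and FMD cannot be sized from the documents, which give no effect or SD for either.

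**3. What reading three outcomes instead of two does to the error rate.** Chance of at least one false positive = 1 − (1 − α)^k, assuming k independent tests, no true effect, and rejection in either direction:

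| Level per test | Two outcomes | Three outcomes |
|---|---|---|
| 0.025 | 1 − 0.975² = 4.9% | 1 − 0.975³ = 7.3% |
| 0.05 | 1 − 0.95² = 9.75% | 1 − 0.95³ = 14.3% |

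Each row isolates the effect of the count. Each column isolates the separate conflict between the 0.025 of Section 4.1 and the 0.05 of Section 4.2. Without independence, the upper bounds (k × α) are 5% and 7.5% in the first row, 10% and 15% in the second.

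**The case against.** The strongest reply is that the plan is clear where it has to be. The synopsis, the Section 3.3 headings and Section 4.1 all point to sleep efficiency and mean nocturnal glucose, and Section 3.1 also has two primary questions. Variability and FMD are expressly secondary. A scientific hypothesis may properly span primary and secondary outcomes; Section 2.2 sits in the Introduction and does not use the word primary. No sentence says that a positive variability or FMD result would count as success.

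Most of this stands, and it rules out several stronger readings that a reader might infer:

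- *That the document holds two competing confirmatory sets.* It does not. No section gives the three hypothesised outcomes a primary label, an alpha or a power calculation. Section 3.3 does not name its three; only the number matches Section 2.2. It could equally reflect the triad of sleep, glycaemic control and vascular dysfunction in Section 2.1.
- *That the primary endpoints do not test the hypothesis at all.* Sleep efficiency is in both.
- *That the trial is too small because alpha should be split three ways.* No document proposes such a split, and the only glucose outcome sized is one the hypothesis omits.
- *That the mismatch raises the false-positive risk from 4.9% to 14.3%.* That comparison changes the number of tests and the threshold together, and the threshold conflict is a separate defect.

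What does not stand is that Section 2.2 is mere background. Its next sentence makes those outcome measures the reason for running the trial, and nothing in Section 4.2 limits which outcomes may support the hypothesis. The misreporting is a possibility the text leaves open; the documents show no intention of it.

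**Conclusion.** The point holds as an inconsistency in the hypothesis and in the count of primaries. The hypothesis and the designated primaries share one outcome, sleep efficiency, and Section 3.3 says three where the lists and the alpha split say two. The sample size needs no change: 34 per arm gives 80.5% power for mean nocturnal glucose at two-sided 0.025, on the protocol's own difference and SD.

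The practical size is what may be claimed at the end. If three outcomes rather than two are treated as carrying the hypothesis, the chance of at least one false positive is 7.3% against 4.9% at 0.025 each, or 14.3% against 9.75% at 0.05 each. These figures assume independence; two glucose measures from the same sensor are likely to be correlated, so they are indicative. It is worth correcting because the correction is small and it closes a route to selective confirmation.

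**What to change.** Four edits to the text:

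1. Section 2.2: state the confirmatory hypothesis as sleep efficiency and 12-day mean nocturnal glucose. Label nocturnal variability and endothelial function as secondary hypotheses that cannot by themselves confirm it.
2. Section 3.1, second primary question: name 12-day mean nocturnal glucose as the measure.
3. Section 3.3, heart rate variability paragraph: change the count of primary outcomes to two.
4. Section 5.91: mark the FMD prediction as a secondary hypothesis, for consistency with the first edit.

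These edits alone do not deliver 4.9%. While Section 4.2 and the synopsis test at P<0.05, two primaries carry 9.75% if independent, so that rule must also be reconciled with 0.025 for the primaries.

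Timing matters. Version 5.1 is dated 31 August 2025, after the estimated primary completion of 01/05/2025. The change should be a dated amendment made before the analyst, who is to be blinded by a second set of study codes (Section 5.4, Randomisation Procedures), is unblinded. If that has already happened, its timing should be disclosed in the report.

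Cost: a few sentences, plus resubmission to the ethics committee, which Section 8 requires for any amendment. Recruitment, conduct and data collection are untouched. The sponsor gives up presenting variability or FMD as confirmation of the main hypothesis; both can still be reported as secondary results.
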